8.1.2.9. Group 1A: Day 31 – Post-vaccine Single Dose Ciprofloxacin PK Session

1. Provide a non-dairy breakfast 30 to 60 min prior to dosing; provide a light lunch and a light dinner/snack over the course of the day.
2. Assess vital signs (seated/semi-recumbent blood pressure, heart rate, respiratory rate and temperature).
3. Collect blood sample for ciprofloxacin $t=0$ concentration determination prior to administration of AM dose of ciprofloxacin.

AV7909 Anthrax Vaccine

IND 014451

Protocol EBS.AVA.210, Version 3.0 (28 October 2019)

4. Administer AM dose of ciprofloxacin following blood sample collection for t=0 concentration determination and record time of administration in the source document and the eCRF; ensure the participant remains semi-recumbent for two hours after dosing and continues with a light activity level throughout the day.
5. Blood samples for ciprofloxacin PK assessment are to be collected at the following time points: 0.25, 0.5, 0.75, 1, 1.5, 2, 2.5, 3, 4, 5, 6, 8, 10 and 12 hours post-dose (± 5 min through hr 4, then ± 15 min thereafter).
6. Administer ciprofloxacin 500 mg po in the clinic after the final 12-hour ciprofloxacin PK sample has been collected and 12 hours after morning dose (± 30 min).
7. Following the PK session, staff will review any changes in concomitant medications.
8. When the participants are discharged from the clinic, they will be reminded:
 - about the diet and activity precautions that must be followed when taking ciprofloxacin (see [Section 5.3](#)).
 - to continue to use the antibiotic e-diary to record their ciprofloxacin doses each day, and to use the reactogenicity e-diary to record any vaccination reactions, if applicable, see [Section 8.3.5.1](#) (Participant e-diary).

8.1.2.10. Group 1A: Days 32, 33 and 34 – Morning

1. Review e-diary, confirm compliance with ciprofloxacin dosing to document compliance, discuss any changes in concomitant medications, as well as any vaccination reactions if still ongoing and remind participants about the dietary and activity precautions that must be followed when taking ciprofloxacin (see [Section 5.3](#)).
2. Collect blood samples for determination of ciprofloxacin trough concentrations prior to the in-clinic administration of the AM dose of ciprofloxacin on Days 32, 33 and 34; record times of administration of ciprofloxacin in source document and the eCRF.
3. On Days 32 and 33, the evening dose (q 12 hr) of ciprofloxacin is to be self-administered at home (at about the same times [± 30 min] each day).
4. Prior to discharge on the morning of Day 34, participants will be reminded to return to clinic that evening for the fourth overnight admission.

8.1.2.11. Group 1A: Day 34 – Evening & Overnight Stay # 4

1. Admit to clinic for overnight stay #4.
2. Staff will review the participant's ciprofloxacin supply and review e-diary entries, conducting a compliance check of the remaining doses compared to the e-diary record. Staff will also ask if the participant required the use of concomitant medication as well as any vaccination reactions if still ongoing.
3. Administer ciprofloxacin 500 mg po 12 hours after morning dose (± 30 min).

AV7909 Anthrax Vaccine

IND 014451

Protocol EBS.AVA.210, Version 3.0 (28 October 2019)

8.1.2.12. Group 1A: Day 35: – Post-vaccine Steady-State Ciprofloxacin PK Session

1. Provide a non-dairy breakfast 30 to 60 min prior to dosing; provide a light lunch and a light dinner/snack over the course of the day.
2. Assess vital signs (seated/semi-recumbent blood pressure, heart rate, respiratory rate and temperature).
3. Collect blood sample for ciprofloxacin t=0 concentration determination prior to administration of AM dose of ciprofloxacin.
4. Administer AM dose of ciprofloxacin (500 mg po) following blood sample collection for t=0 concentration determination and record time of administration in the source document and the eCRF; ensure the participant remains semi-recumbent for two hours after dosing and continues with a light activity level throughout the day.
5. Blood samples for ciprofloxacin PK assessment are to be collected at the following time points: 0.25, 0.5, 0.75, 1, 1.5, 2, 2.5, 3, 4, 5, 6, 8, 10 and 12 hours post-dose (± 5 min through hr 4, then ± 15 min thereafter).
6. Administer ciprofloxacin 500 mg po in the clinic after the final 12-hour ciprofloxacin PK sample has been collected and 12 hours after the morning dose (± 30 min).
7. Record concomitant medications.
8. Return ciprofloxacin supply to participant
9. When the participants are discharged from the clinic, they will be reminded:
 - about the diet and activity precautions that must be followed when taking ciprofloxacin (see [Section 5.3](#)).
 - to continue to use the antibiotic e-diary to record the times they take their ciprofloxacin doses each day and to use the reactogenicity e-diary to record any vaccination reactions, if applicable, see [Section 8.3.5.1](#) (Participant e-diary).

8.1.2.13. Group 1A: Day 36 (At home)

Two ciprofloxacin doses (500 mg po morning and evening, q 12 hr) are to be self-administered at home on Day 36. The participant will continue with the e-diary as described in [Section 8.3.5.1](#).

8.1.2.14. Group 1A: Day 37 (± 1 d) – Blood Draw for TNA

The Day 37 visit to draw blood for immunogenicity may shift by ± 1 d. If such a shift in visit day occurs, the participant must remain on ciprofloxacin 500 mg po every 12 hours until the morning of that visit. In the event of such a shift, the participant's required number of doses of ciprofloxacin will vary. The Pharmacy Manual will contain a table detailing the dosing options for the final course of ciprofloxacin given a one-day shift from Day 37.

1. Participants will report to the clinic having taken their morning dose of ciprofloxacin at home.

AV7909 Anthrax Vaccine

IND 014451

Protocol EBS.AVA.210, Version 3.0 (28 October 2019)

2. Review participant's ciprofloxacin supply; count the number of remaining doses and compare to the e-diary record to document compliance; record total remaining in source document and eCRF.
3. Review other e-diary entries with participant. Discuss any changes in the use of concomitant medication as well as any vaccination reactions if still ongoing. Remind participants that they should still use sunscreen and avoid excessive sun exposure and strenuous sports until the Day 51 Final Study Visit.
4. Record concomitant medications.
5. Collect blood sample for TNA assessment.

8.1.2.15. Group 1A: Day 51 (\pm 1d) – Final In-Clinic Study Visit

1. Perform complete PE.
2. Review e-diary entries with participant and collect hand-held device if study provided.
3. Review and record AEs.
4. Record concomitant medications.
5. Assess vital signs (seated/semi-recumbent blood pressure, heart rate, respiratory rate and temperature).
6. For WOCBP, collect and perform a UPT. Positive UPTs will be confirmed with a serum pregnancy test. All confirmed pregnancies in participants who receive at least one dose of AV7909 or ciprofloxacin and where conception occurs prior to 12 months after last receipt of either IP will be followed to outcome.
7. Collect blood samples for hematology and serum chemistry.
8. Collect blood samples for TSH & autoantibodies.
9. Collect urine sample for urinalysis.

8.1.3. Group 1B: Ciprofloxacin + AV7909 without Ciprofloxacin PK

Shown in [Table 6](#) is a schedule of events for Group 1B participants from screening until the end of the study. Following the table are detailed descriptions of the activities that the sites are expected to conduct for each of the column headings identified in the table once each participant has received his or her group assignment. Note that this detail starts following randomization for Group 1B which is when they receive their first course of ciprofloxacin although the actual activities for the trial do not begin until Day 4 when participants self-administer their first dose

AV7909 Anthrax Vaccine

IND 014451

Protocol EBS.AVA.210, Version 3.0 (28 October 2019)

of ciprofloxacin. The detailed activities during Screening and Group Assign (Randomization) were covered previously in [Section 8.1.1](#).

Table 6: Schedule of Events for Group 1B: Ciprofloxacin + AV7909 without Ciprofloxacin PK

	Screening	Group Assign	At Home†	Vac	At Home†	TNA	Final Visit	Safety Calls	EWV USV‡
Study Day(s)	-28 to -2	1	4-7	8 23*	9, 22, 24, 31-37	37	51	114, 205, 296, 388	NA
Visit Window	NA	NA		*± 1 d		± 1 d	± 1 d	± 14 d	
Sign, date ICF & assign ID	X								
Review eligibility ^a	X	X		X					
Medical history & demographics	X	X							
Physical examination ^b	X						X		X
ECG ^c	X								
Vital signs ^d	X	X		X			X		X
Pregnancy test ^e	X	X		X			X		X
FSH test ^e	X								
Collect sample for hematology ^f	X						X		X
Collect sample for serum chemistry ^g	X						X		X
Collect sample for urinalysis ^h	X						X		X
Urine drug screen ⁱ	X								
HIVAb/HBsAg/HCVAb	X								
Concomitant medications ^j	X	X		X		X	X	X	X
Randomize eligible participants		X							
Symptom-directed PE ^k		X		X					
Blood draws for TNA ^l		X				X			
Cipro dosing & compliance ^{m,n}		X	X	X	X	X			X ⁿ
AV7909 vaccination ^o				X					
Participant e-diary + tools ^p		X	X	X	X	X	X		X
Staff review of e-diaries ^q			X	X	X	X	X		X
AEs ^r , SAEs & AESIs ^s	X	X		X			X	X	X
Collect TSH & autoantibody samples ^t		X					X		X

For the abbreviations used above please refer to [Table 1](#) of the protocol. *The ± 1 d window applies only to the second vaccination on Day 23 (note: the second course of antibiotic treatment will have to shift accordingly). †At Home Days are only those days where both doses of ciprofloxacin are taken at home. ‡For EWV occurring within the visit window of Day 37, a blood sample for TNA will be drawn.

^a Eligibility will be reviewed before each vaccination, ie, on Day 8 and Day 23.

^b Physical examinations (PE) will be conducted as described in [Protocol Section 8.3.3](#).

^c ECGs will be conducted and interpreted at screening as described in [Protocol Section 8.3.3](#).

^d Vital signs will be administered as described in [Protocol Section 8.3.4](#).

^e Pregnancy tests (serum and/or urine) will be administered to all WOCBP as described in [Protocol Section 8.3.2](#). Serum pregnancy test will be performed at Screening visit for WOCBP, while urine pregnancy tests for WOCBP will be required before each vaccination. At Screening visit only, FSH test will be performed for postmenopausal women.

^f Hematology will be conducted as described in [Protocol Section 8.3.2](#).

AV7909 Anthrax Vaccine

IND 014451

Protocol EBS.AVA.210, Version 3.0 (28 October 2019)

^g Serum chemistry will be conducted as described Protocol Section 8.3.2.

^h Urinalysis will be conducted as described in Protocol Section 8.3.2.

ⁱ Urine drug screens will be conducted as described in Protocol Section 8.3.2.

^j Concomitant medications will be identified and recorded as described in Protocol Section 6.5.

^k Symptom-directed PEs will be conducted as described in Protocol Section 8.3.3.

^l Blood samples for TNA assessment on Day 1 will be collected in the morning following randomization. Those on Day 37 will be collected after the final dose of ciprofloxacin has been administered. A TNA sample will also be collected if EWV occurs within the visit window of Day 37 as described in Protocol Section 8.1.8.

^m Participants receive their first course of ciprofloxacin following randomization. Format of the doses and distribution of subsequent courses will be described in the Pharmacy manual. Self-administration of ciprofloxacin starts on Day 4. Ciprofloxacin dose compliance will be managed as described in Protocol Section 6.4.

ⁿ Ciprofloxacin doses (500 mg po q 12 hr) will be administered as described in Protocol Section 6.1.2.

^o Vaccinations with AV7909 will be administered as described Protocol Section 6.1.4.

^p All participants will be provided with an e-diary for post vaccination follow up along with a thermometer and an injection site reaction measurement tool. Participants in Group 1 and 2 will be provided with an e-dairy for antibiotic compliance. All participants will be trained on the use of these tools and the e-diaries as described in Protocol Section 8.3.5.1.

^q Staff will begin reviewing the e-diaries on Day 5 and will review them at regular intervals thereafter.

^r AEs will be collected at all clinic visits through Day 51/EWV as described in detail in Protocol Section 9.

^s AEs, SAEs and potential AESIs will be collected during the Safety Follow-Up Telephone Calls (see Protocol Section 8.1.7).

^t Serum samples for TSH & autoantibody testing will be collected from all participants and tested as described in Protocol Section 8.3.2 (ie, at Day 1, Day 51, and at EWV if the subject received at least one vaccination). Additional samples for TSH & autoantibody testing may be requested (ie, based on the participant's report(s) of a potential AESI); blood draws for additional TSH and/or autoantibody testing should be performed as part of an unscheduled visit.

8.1.3.1. Group 1B: Days 4 to 7 (At home)

1. On Days 4 to 7, the participant will self-administer ciprofloxacin 500 mg po every 12 hours at home at about the same times (\pm 30 min) each day.
2. Participant will use the antibiotic e-diary to record the date and time of administration of ciprofloxacin.

8.1.3.2. Group 1B: Day 8 – Vaccination #1

1. Review eligibility.
2. Staff will review the ciprofloxacin supply and review the e-diary entries, conducting a compliance check of the remaining doses compared to the e-diary record. Staff will record ciprofloxacin doses to document compliance. Staff will also discuss any changes in the use of concomitant medication while reminding the participant of the precautions in Section 5.3.
3. Review and record AEs.
4. Conduct a symptom-directed PE, if required.
5. Assess vital signs (seated/semi-recumbent blood pressure, heart rate, respiratory rate and temperature).
6. For WOCBP, collect and perform UPT (prior to AV7909 vaccination). Positive UPTs will be confirmed with a serum pregnancy test. All confirmed pregnancies in participants who receive at least one dose of AV7909 or ciprofloxacin and where conception occurs prior to 12 months after last receipt of either IP will be followed to outcome.

AV7909 Anthrax Vaccine

IND 014451

Protocol EBS.AVA.210, Version 3.0 (28 October 2019)

7. Administer ciprofloxacin 500 mg po in AM prior to vaccination; the evening dose of ciprofloxacin 500 mg po will be self-administered at home 12 hours after the AM dose [and at approximately the same time (± 30 min) each day].
8. Administer AV7909 vaccination #1. Participants should be monitored for at least 30 minutes following vaccine administration for any adverse effects especially anaphylaxis.
9. Assess vital signs at 30 ± 5 min postvaccination.
10. Prior to being discharged from the clinic, the participant will be given and trained on an e-diary to capture local and systemic reactogenicity events (ie, reactogenicity e-diary) and to record daily for at least seven days following each vaccination. If a reaction is not resolved at seven days postvaccination, the participant is to continue completing the e-diary daily until they are symptom free for two consecutive days. Participants will be given an injection site reaction measurement tool and shown how to use it to measure the size and assess the severity of certain reactogenicity events associated with vaccination. See [Section 8.3.5.1](#) (e-diary) and remind participants about the diet and activity precautions that must be followed when taking ciprofloxacin (see [Section 5.3](#)).

8.1.3.3. Group 1B: Days 9, 22 and 24 (At home)

On Days 9, 22 and 24, the participant is to self-administer ciprofloxacin (500 mg po q 12 hr) at home [at about the same times (± 30 min) each day]. The participant will continue with the e-diary as described in [Section 8.3.5.1](#).

It is required that participants self-administer ciprofloxacin on the day before (morning and evening), the day of (evening), and the day after (morning and evening) vaccination. The site must contact the participant to remind them to begin their second course of the antibiotics (ie, the site should contact the participant within 24 hours of the anticipated start day for the second course of antibiotics in relation to the scheduled second vaccination date). Any participant who schedules vaccination 2 (on Day 23) to shift within the allowable window (± 1 d) will be reminded to start their ciprofloxacin dosing on the appropriate day, eg, if the second vaccination shifts to Day 22 then the participant will be reminded to start taking ciprofloxacin on the morning and evening of Day 21 in order to meet the dosing requirement.

8.1.3.4. Group 1B: Day 23 (± 1 d) – Vaccination #2

1. Staff will review ciprofloxacin supply and review against e-diary entries conducting a compliance check of the remaining doses compared to the e-diary record. Staff will record ciprofloxacin doses to document compliance. Staff will discuss changes in the use of concomitant medication as well as any vaccination reactions if still ongoing while reminding the participant of the precautions in [Section 5.3](#).
2. Review and record AEs.
3. Perform symptom-directed PE, if required.
4. Record concomitant medications.
5. Assess vital signs (seated/semi-recumbent blood pressure, heart rate, respiratory rate, and temperature).

AV7909 Anthrax Vaccine

IND 014451

Protocol EBS.AVA.210, Version 3.0 (28 October 2019)

6. Review eligibility for continuing vaccination.
7. For female participants not exempted due to a screening FSH >30 mIU/mL, collect and perform UPT (prior to AV7909 vaccination). Positive UPTs will be confirmed with a serum pregnancy test. All confirmed pregnancies in participants who receive at least one dose of any IP and where conception occurs prior to 12 months after last receipt of any IP will be followed to outcome.
8. Administer ciprofloxacin 500 mg po in AM; the evening dose will be self-administered at home.
9. Administer AV7909 vaccination #2; this should occur after ciprofloxacin dosing. Participants should be monitored for at least 30 minutes following vaccine administration for any adverse effects especially anaphylaxis.
10. Following the 30 (\pm 5) minutes of observation, repeat vital signs (seated/semi-recumbent blood pressure, heart rate, respiratory rate, and temperature) measurement.
11. After e-diary review, participants will be reminded to continue to use the reactogenicity e-diary and injection site reaction measurement tool to capture the adverse events associated with vaccination, and to record the dates and times they self-administer their ciprofloxacin doses in the antibiotic e-diary. See [Section 8.3.5.1](#) (e-diary).
12. Prior to discharge on Day 23, participants will be reminded to return to clinic in two weeks (\pm 1 d) on Day 37 \pm 1 d for the final blood draws for TNA. Again, participants are to continue dosing with ciprofloxacin through the evening of Day 24 and discontinue dosing until Day 31. Their ciprofloxacin supply will be returned to them before they are discharged from the clinic.

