### 3.4 Analysis Time Points

Participant visits occur on protocol-specified days with associated visit windows. The schedule may shift by  $\pm 1$  day at the following visits:

- Day 23 visit of the second vaccination for all participants.
- Day 37 visit of TNA assessment for Group 1, 2B, and 3. There is no shifting flexibility for Group 2A at this visit as PK assessment schedule at Day 38.
- Day 51 of final study visit for all participants.

If not otherwise specified, for the purposes of analysis, the analysis visits will be assigned as provided in **Table 2** for vaccination, immunogenicity (TNA) testing, clinical laboratory data,

vital signs, and physical examinations. Data at unscheduled visits will not be presented in the by-visit summary analyses but will be included in the summary tables by maximum toxicity grade or abnormality when applicable, and in data listings.

**Table 2 Analysis Windows for Vaccination, Immunogenicity (TNA) Testing, Clinical Laboratory Data, Vital Signs, and Physical Examinations**

Analysis Visit	Nominal Day	Lower Limit of Study Day	Upper Limit of Study Day
Baseline	NA	-28	Prior to the first exposure to any study treatment
Day 1	1	1	1
Day 8	8	8	8
Day 23	23	22	24
Day 37	37	36 for Group 1, 2B, and 3, 37 for Group 2A	38 for Group 1, 2B, and 3, 37 for Group 2A
Day 51	51	50	52

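### Group 1B's discharge instruction ends the second ciprofloxacin course on calendar Day 24: this conflicts with the vaccination-anchored course if vaccination 2 is on Day 24, and overruns it by one day if it is on Day 22

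*Protocol*

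**What the plan says.** Three places in the protocol describe when Group 1B's second ciprofloxacin course ends.

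- **Section 8.1.3.3** states a requirement relative to the vaccination: "participants self-administer ciprofloxacin on the day before (morning and evening), the day of (evening), and the day after (morning and evening) vaccination". The morning dose on the vaccination day is given in clinic (Section 8.1.3.4, item 8). A worked example of a shift follows, and it concerns only the start of the course: for vaccination on Day 22, dosing starts on Day 21.
- **Table 6, footnote on the ± 1 d window**: if vaccination 2 moves, "the second course of antibiotic treatment will have to shift accordingly".
- **Section 8.1.3.4, item 12**, under a heading that allows Day 23 ± 1 d, gives a fixed stop: "participants are to continue dosing with ciprofloxacin through the evening of Day 24 and discontinue dosing until Day 31".

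The matching discharge steps for Group 1A (Section 8.1.2.7) and Group 2A (Section 8.1.4.7) are relative. Both point to the day after the visit, and Group 1A's adds Day 24 in brackets.

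Item 12 also sets the toxin-neutralizing antibody (TNA) visit. It opens "Prior to discharge on Day 23, participants will be reminded to return to clinic in two weeks", allows ± 1 d on the two weeks, and in the same phrase gives Day 37 ± 1 d.

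**The concern.** Two operative instructions, both addressed to the same participants, give different end dates for the course on visit days that the protocol allows. Antibiotic exposure around vaccination 2 is part of the condition whose effect on Day 37 TNA the Group 1 versus Group 3 non-inferiority comparison examines. Group 1B is also mostly self-dosed (29 of 31 doses at home), so the discharge instruction matters. A participant vaccinated on Day 24 who follows item 12 takes nothing on the day after vaccination. One who follows Section 8.1.3.3 takes two doses then. The exposure being tested would depend on which sentence the site reads out.

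**Working it through.** **Inputs**

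- Course 1: Days 4–9 (Protocol Section 4.1.2).
- Course 2: vaccination day *v* − 1 to *v* + 1 (Section 8.1.3.3), with *v* = 22, 23 or 24.
- Course 3: Day 31 to the morning of the TNA visit on day *d* (Section 8.1.3.6; the Figure 1 footnote drops the Day 37 evening dose).
- Stated total: 31 ± 2 (Section 6.1.5).

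**Reproducing the plan's figure.** Course 1 is 2 × 6 = 12. Course 2 is 2 × 3 = 6. Course 3 with *d* = 37 is 2 × (37 − 31) + 1 = 13. The total is 12 + 6 + 13 = 31, an exact match. Moving the TNA visit by one day gives 29 or 33, which accounts for the ± 2.

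**Item 12 read literally.** Item 12 does not state a start, so the start stays at *v* − 1. Course 2 is then 2 × (24 − (*v* − 1) + 1) = 2 × (26 − *v*).

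| Vaccination 2 | Course 2 days, 8.1.3.3 | Doses | Course 2 days, item 12 | Doses | Difference |
|---|---|---|---|---|---|
| Day 22 | 21–23 | 6 | 21–24 | 8 | +2 (Day 24) |
| Day 23 | 22–24 | 6 | 22–24 | 6 | 0 |
| Day 24 | 23–25 | 6 | 23–24 | 4 | −2 (Day 25) |

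For Day 24 the conflict is direct: one passage requires two doses on Day 25 and the other says to have stopped. For Day 22 the three required days are all covered, and the extra day departs only from the statement that the course shifts.

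**Totals under item 12**, as 12 + course 2 + 2 × (*d* − 31) + 1:

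| Vaccination 2 | TNA Day 36 | TNA Day 37 | TNA Day 38 |
|---|---|---|---|
| Day 22 | 31 | 33 | 35 |
| Day 23 | 29 | 31 | 33 |
| Day 24 | 27 | 29 | 31 |

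With a Day 37 visit the totals stay within 31 ± 2. With a shifted visit they can reach 27 or 35. The Immunogenicity Population threshold is 50% of doses, 0.5 × 31 = 15.5, and even 27 is well above it.

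**TNA visit wording.** Two weeks ± 1 d is *v* + 13 to *v* + 15: Days 35–37, 36–38 and 37–39 for vaccination on Day 22, 23 and 24. The calendar window is Days 36–38 throughout. The two coincide only for Day 23, but they always overlap, and Day 37 satisfies both in every case.

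**The case against.** The best defence is that item 12 describes the nominal schedule. It is worded for discharge on Day 23, and its dosing reminder is introduced as a repetition of earlier text. Group 1A's step shows Day 24 being used as a label for the day after a Day 23 vaccination. Section 8.1.3.3 is expressed as a requirement, and Table 6 moves the whole course. Doses are also logged with date and time and tablets counted, so a departure could be seen.

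Most of this stands. Nominal wording is the likely origin, and the Day 22 case is weak. What it does not remove is the Day 24 conflict. Item 12 sits under a heading that admits Day 24, and it is the discharge instruction at that visit. The worked example in Section 8.1.3.3 says nothing about the end of the course. The Pharmacy Manual table promised in Section 8.1.3.6 covers the final course, not the second. The e-diary issues dosing reminders, but the documents do not say that their schedule moves with vaccination 2.

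A reader might also infer that the TNA window is wrong and should become 13–15 days after the actual vaccination. The documents do not support that:

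- The endpoint attaches its ± 1 d to Day 37, and Protocol Section 8.2, Section 8.1.3.6 and Table 6 do the same. SAP Table 2 follows with a lower limit of "36 for Group 1, 2B, and 3" and an upper limit of 38, counted from randomization.
- No separate vaccination-anchored TNA window exists to be contradicted.
- Groups 2B and 3 carry the same wording as Group 1B, so nothing differential between the arms is shown.
- Re-anchoring Group 1B alone would separate it from its comparator. It would also change dosing, because ciprofloxacin runs to the morning of the visit: a Day 35 visit gives 12 + 6 + 9 = 27 doses and a Day 39 visit gives 12 + 6 + 17 = 35, both outside 31 ± 2.

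**Conclusion.** The point holds as a minor wording inconsistency. For vaccination 2 on Day 24, item 12 and Section 8.1.3.3 cannot both be followed, and two doses are at issue. For Day 22, item 12 adds two doses beyond the shifted course without missing a required day. For Day 23 there is no difference.

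This rests on reading item 12 literally under its Day 23 ± 1 d heading. The number affected is unknown. As an assumption only, if 10% to 30% of the 30 planned Group 1B participants moved vaccination 2, that would be 3 to 9 people, and only those moved to Day 24 would meet the firm conflict.

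Two stronger conclusions might be drawn, and neither is supported. One is that the difference cannot be detected because totals stay inside 31 ± 2. That is true only with a Day 37 visit, and dated dose records exist in any case. The other is that the non-inferiority result is compromised: no effect on power, type I error or membership of the Immunogenicity Population through the 50% criterion is shown.

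**What to change.** Reconcile item 12 of Section 8.1.3.4 with Section 8.1.3.3 and the Table 6 footnote, so that one statement governs when the second course ends if vaccination 2 moves to Day 22 or Day 24. The sponsor must decide what that statement is; no dosing rule is proposed here.

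The cost is about one sentence in the protocol and a notice to sites. The SAP, the sample size and the TNA analysis window need no change. At most, the sponsor could note that the two expressions for the TNA visit coincide only when vaccination 2 is on Day 23. That wording is shared by Groups 1B, 2B and 3, so any tidying should be made in all three together.
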